5.3 Data Handling

5.3.1 Premature Withdrawal and Missing Data

Subjects who prematurely withdraw from the study will be included in analyses up to the time of withdrawal, regardless of the duration of treatment and survival follow-up.

Missing data occurs when any requested data is not provided, leading to blank field on the collection instrument. These data will be indicated using a “blank” in subject data listings. Answers such as “Not applicable” and “Not evaluable” are not considered to be missing data and should be displayed as such.

Subjects with unknown or missing best response will be assumed to be non-responders and will be included in the denominator when calculating percentages. Subjects with the designation of treatment relationship for adverse events (AEs) and serious adverse events (SAEs) missing will have the worst case assumed to impute the relationship: if the relationship to study treatment is missing, it will be assumed to be “Yes” for summary of drug-related AE or SAE.

For the time to event endpoints including DOR and PFS, the missing data handling method will be censoring. Censoring mechanisms for these endpoints are described in section **Error! Reference source not found..**

The length of study treatment for each subject will depend on the safety, tolerability, and efficacy of the treatment, so the duration of treatment will vary across subjects. Subjects with shorter duration of treatment due to the natural history of their disease or medical necessities of treatment of their disease will not be considered to have missing data.

5.3.2 Baseline and Change from Baseline

Unless otherwise specified, the baseline value is defined as the last value obtained on or before the date and time of the first SL-172154 dose on Cycle 1 Day (C1D1). Post-baseline values are defined as value obtained after the first dose of SL-172154. Change from baseline is calculated as: (post-baseline value - baseline value). The percent change from baseline is calculated as: (change from baseline/baseline value) *100. If either baseline or post-baseline value is missing, the change from baseline and percent change from baseline is set to be missing as well.

5.3.3 Study Day and Duration

The reference date for age calculation is the date of consent form signed as age is an eligibility requirement. The reference date for safety, efficacy and other data analyses is the date of the first dose.

- **Study Day** – Study Day 1 is defined as the date of the first dose; the day before the first dose is defined as Study Day -1. For a given event date, Study Day is calculated relative to the date of first dose of study drug.

Study Day = [Event Date – First Dose Date] (in days) + 1 day,
where the event date is on or after the first dose date.

Study Day = [Event Date – First Dose Date] (in days),
where the event date is before the first dose date.

- **Duration (Days)** – A duration in days is calculated as the number of days between one date (Date1) and another later date (Date2)

Duration (days) = [Date2 – Date1] (in days) + 1 day.

- **Duration (Months)** – A duration in months is calculated as the duration in days divided by 365.25/12, rounded to one decimal place.
- **Duration (Years)** – A duration in years is calculated as the duration in days divided by 365.25, rounded to one decimal place.

5.3.4 Imputation of Partial Date

In general, imputed partial dates will not be used to derive study day or duration variables. In addition, imputed partial dates are not used for the time to event endpoint analysis. However, partial dates may be imputed for exploratory analysis. The imputed partial data will be flagged in

the dataset to indicate the level of imputation. Imputed dates will not be displayed in the data listings.

6. STUDY POPULATION

Unless specified otherwise, all summary tables and data listings for the study population will be based on the All Treated Population.

6.1 Subject Disposition

Summaries of study population and subject disposition will include the number of subjects in each analysis population, the number of subjects by study status, and the primary reason for study completion/discontinuation. Study population and subject disposition information will be presented in a data listing. Both summary table and listing will be based on the Enrolled population.

Summaries of study treatment status will include the number of subjects by treatment status, and the primary reason for study treatment discontinuation. Subject treatment discontinuation information will be presented in a data listing.

6.2 Protocol Deviations

Number of subjects for each protocol deviation type and subtype will be summarized for all protocol deviation and key protocol deviations, respectively. Protocol deviations will be tracked by the study team throughout the conduct of the study in accordance with the Protocol Deviation Management Plan. A listing with deviation details will be provided for all protocol deviations.

6.3 Demographic

Demographic variables include age, sex, ethnicity, race, and weight and height at screening. Descriptive statistics will be presented for age, weight, and height. Frequency counts and percentages will be presented for age groups (<18 years, 18 to <65 years, 65 to <75 years and \geq 75 years), sex, ethnicity, and race. All demographic data will be presented in a data listing for All Treated subjects.

6.4 Study Cancer History

General study cancer history information including the tumor type, human papilloma virus status, and time since initial diagnosis will be summarized in tables. In addition, primary anatomic site of tumor and extent of disease will be summarized for CSCC; and primary anatomic site of tumor, stage at study entry, and status of tobacco use will be summarized for SCCHN. All study cancer history data will be presented in a data listing.

6.5 General Medical and Surgical History

General medical history and surgical history along with start/end date and ongoing status at study entry will be presented in a data listing.

6.6 Prior Anti-Cancer Treatment

Prior study cancer systemic treatment drugs will be coded using the World Health Organization (WHO) Drug Dictionary. Prior study cancer systemic treatment including regimen number, drug name, start/end date, duration, intent, best response, and data of progression on the most recent regimen will be presented in a data listing. The number of prior systemic regimens for all intents, and number of prior systemic regimens for advanced/metastatic disease will be included in the summary table. Summary will be provided by dose levels/cohorts and all subjects in the analysis population.

Prior anti-cancer surgical treatment including the date and intent of procedure will be presented in a data listing. Prior anti-cancer radiotherapy including the start/end date and intent of radiotherapy will be presented in a data listing.

6.7 Study Drug Exposure

The individual subject SL-172154 ITI administration at each dosing visit will be provided in a data listing. This listing will include assigned dose level, study drug lot number, total dose injected (mg), total volume injected, injection date, start/end of injection time, injection outcome and overdose assessment along with reason. For each target, non-target and new lesion at each dosing visit, the lesion number, location, injection administration status (Yes/No), injected volume, and administration method will also be included in the data listing.

The following SL-172154 ITI administration information will be summarized:

- Number of doses received, which is the total number of dosing visits with non-zero dose injected.
- Duration of SL-172154 treatment is defined as:
 - Minimum of (data cutoff date plus 1 day or date of last dose + 21 days if last dose is C2D1 or beyond or + 7 days if last dose is C1D1, C1D8 or C1D15) minus date of first study drug administration for subjects who are on treatment.
 - Minimum of (date of death plus 1 day, data cutoff date plus 1 day, or date of last dose + 14 days if last dose is C2D1 or beyond or + 7 days if last dose is C1D1, C1D8 or C1D15) minus date of first study drug administration for subjects who discontinued from treatment.

In addition to mean, median, minimum and maximum, duration on treatment will also be summarized as <6 weeks, >=6 to <12 weeks, and >=12 weeks.

Individual duration of SL-172154 treatment will be plotted using horizontal bar graph with information on dose level, cancer type, time of responses (RECIST 1.1), best response and treatment status for each subject.

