3.4 Dose Escalation of SL-172154 Administered by Intratumoral Injection

Dose escalation will proceed using a flat dose and fixed volume format (see Section [6.8](#) for additional details). Dose escalation will begin at the starting dose of 0.003 mg as outlined in [Table](#)

[figure not shown]
1 below; intermediate dose levels not shown may be explored based on emerging data (e.g., safety). Dose escalation of intratumoral SL-172154 will not exceed half-log increments. The DLT assessment period is 21 days in length and encompasses the first 21-day cycle of therapy. Dose escalation will follow mTPI-2 decision rules outlined in [Table 5](#) in Section 9.1.

- Dose escalation in half-log increments ([Table 1](#))
- Schedule of administration for ITI of SL-172154: Doses administered on days 1, 8, 15 of a 21-day cycle in cycle 1 and on day 1 of each subsequent 21-day cycle, starting on cycle 2, day 1 (day 22) ([Figure 2](#)).
- Cycle length: 21 days
- DLT assessment period: 21 days of cycle 1

Table 1: Intratumoral Dose Escalation Plan for SL-172154

Dose Level	ITI Dose (mg) of SL-172154 ^a	ITI Volume of Dose
Level 1 - starting dose	0.003	1.5 mL
Level 2	0.01	1.5 mL
Level 3	0.03	1.5 mL
Level 4	0.1	1.5 mL
a) Intermediate or higher dose levels may be tested based on emerging safety and/or pharmacodynamic data. Dose escalation will not exceed half-log increments.		

Figure 2: ITI Schedule for SL-172154

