3.1 Study Design

This trial is designed to evaluate the safety, PK, anti-tumor activity and pharmacodynamic effects of SL-172154 administered by ITI on days 1, 8, 15 of a 21-day in cycle 1 and then on day 1 of each subsequent 21-day cycle (cycles ≥ 2). Subjects that are eligible for enrollment have locally advanced or metastatic CSCC or SCCHN that is not amenable to further treatment with surgery, radiation or standard systemic therapies that are known to provide clinical benefit for their condition (see Schema below).

Study Design: Phase 1 Study of SL-172154 (SIRPa-Fc-CD40L)

Administered Intratumorally

Primary objectives: Safety and tolerability of SL-172154 given intratumorally

Secondary objectives: RP2D, PK, immunogenicity, anti-tumor activity / **Exploratory objectives:** PD markers in blood and tumor

Tumortype: Subjects with locally advanced or metastatic CSCC or HNSCC not amenable for standard therapy

Dose Escalation Study (N ~ 18 Subjects)					
Dose Escalation Rules:	mTPI-2	Dose Level	SL-172154 ITI Dose (mg)	PD Cohort	RP2D Decision
DLT Assessment Period:	21 days	Start: 1	0.003		Based on totality of data
Subjects per Cohort:	≥ 3	2	0.01	Further assessment of SL-172154 at ITI dose that has been cleared for safety	Safety, PK, PD and anti-tumor activity
	(n ~ 12 subjects)	3	0.03		
		4	0.1	(n ~ 6 subjects)	

SL-172154 Dosing Schedule

Cycle 1: Once weekly intratumoral administration for 3 weeks (D1, D8, D15) in first 21 days

Beyond: Starting C2D1 (day 22) dosing will occur on D1 of each 21-day cycle

Dose Escalation Cohorts

[figure not shown]
Dose escalation will utilize the modified Toxicity Probability Interval (mTPI-2) design with target DLT rate of 30% for the MTD as described by Guo et al. Subjects will be enrolled in cohorts of approximately 3 subjects into sequential dose levels of SL-172154 and evaluated for DLT during the 21-day DLT evaluation period starting from the first dose of SL-172154. At each dose level, a minimum 3-day stagger between dosing the first and second subject is required. Dose escalation will proceed using a flat dose and fixed volume format with the starting dose of 0.003mg. The planned dose escalation is in half-log increments as outlined in Table 1. The DLT assessment period is 21 days in length and encompass the first 21-day cycle of study treatment. The ITI schedule is outlined in Figure 1.

Table 1: Intratumoral Dose Escalation Plan for SL-172154

Dose Level	ITI Dose (mg) of SL-172154 ^a	ITI Volume of Dose

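### Treatment duration for discontinued subjects credits 14 days after a cycle 2 or later dose, although the dosing interval is 21 days

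*SAP*

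**What the plan says.** SAP 6.7 (Study Drug Exposure) defines duration of treatment in two bullets. Each takes the earliest of several end dates and subtracts the date of first dose.

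- Subjects on treatment: the candidate end dates are data cutoff plus 1 day and, from cycle 2, "date of last dose + 21 days if last dose is C2D1 or beyond".
- Discontinued subjects: the list begins "Minimum of (date of death plus 1 day, data cutoff date plus 1 day" and continues, from cycle 2, with "date of last dose + 14 days if last dose is C2D1 or beyond".
- After a cycle 1 dose both bullets add the same amount: "7 days if last dose is C1D1, C1D8 or C1D15".

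The same section reports the result in categories: "duration on treatment will also be summarized as <6 weeks, >=6 to <12 weeks, and >=12 weeks". It also calls for a horizontal bar plot of each subject's duration, showing dose level, response and treatment status.

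On the schedule, SAP 3.1 says "Starting C2D1 (day 22) dosing will occur on D1 of each 21-day cycle" and Protocol 3.4 says "Cycle length: 21 days".

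**The concern.** Three of the four constants in the definition equal the interval to the next scheduled dose: 7 days in weekly cycle 1 (in both bullets) and 21 days from cycle 2 (on-treatment bullet). The 14 is the exception and matches no dosing interval in the trial. Once the data cutoff is far enough past the last dose, two subjects with identical dosing get different durations only because one is recorded as discontinued.

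SAP 1 states that enrollment ended early, as of 24 February 2022, and that the SAP was revised because the study was stopped prematurely. Termination by the sponsor is itself a reason to stop treatment (SAP 3.4). Most subjects are therefore likely to fall under the discontinued rule at the final analysis, though the documents give no counts.

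Duration feeds Table 14.3.1.1 and Figure 14.2.1. Summaries are by dose level and cohort (SAP 5.2), with about 3 subjects per escalation cohort (SAP 3.1), so one reclassified subject can move a third of a dose-level row. In the figure, bars built on two rules would share one axis.

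**Working it through.** **Inputs**

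- Days added from C2D1 on: 14 if discontinued, 21 if on treatment (SAP 6.7).
- Days added in cycle 1: 7 in both bullets (SAP 6.7).
- Dosing days: 1, 8, 15, 22, 43, 64 (Protocol 6.1), then every 21 days.
- Category cuts: 6 weeks = 42 days, 12 weeks = 84 days.
- Dosing window after C2D1: plus or minus 3 days (Protocol 6.1, footnote m).

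**Step 1. Interval to the next scheduled dose**

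- After C1D15: 22 − 15 = 7 days, which reproduces the 7-day constant.
- After C2D1: 43 − 22 = 21 days. After C3D1: 64 − 43 = 21 days. These reproduce the on-treatment constant.
- The 14 cannot be reproduced. Shortfall: 21 − 14 = 7 days.

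**Step 2. Duration by last dose** (on schedule, no truncation by death or cutoff)

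C(n)D1 falls 21 × (n − 1) days after the first dose, so duration = 21 × (n − 1) + constant.

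| Last dose | With 14 | With 21 | Category with 14 | Category with 21 | Loss |
|---|---|---|---|---|---|
| C2D1 | 21 + 14 = 35 | 21 + 21 = 42 | under 6 weeks | 6 to under 12 | 7/42 = 17% |
| C3D1 | 42 + 14 = 56 | 42 + 21 = 63 | 6 to under 12 | 6 to under 12 | 7/63 = 11% |
| C4D1 | 63 + 14 = 77 | 63 + 21 = 84 | 6 to under 12 | 12 or more | 7/84 = 8% |
| C5D1 | 84 + 14 = 98 | 84 + 21 = 105 | 12 or more | 12 or more | 7/105 = 7% |

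Last doses in cycle 1 give 7, 14 and 21 days under either bullet and are unaffected.

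**Step 3. When the category changes**

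Let d be the days from first to last dose. The category differs when d + 14 < 42 ≤ d + 21, that is d = 21 to 27, or when d + 14 < 84 ≤ d + 21, that is d = 63 to 69. A C4D1 dose on time or up to 3 days late (d = 63 to 66) is reclassified. One given 1 to 3 days early (d = 60 to 62) is not.

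**Step 4. Truncation**

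Let k be the days from last dose to the earlier of death and data cutoff. The days credited are min(k + 1, 14) against min(k + 1, 21).

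- k ≤ 13: no difference.
- k = 14 to 19: difference k − 13, that is 1 to 6 days.
- k ≥ 20: the full 7 days.

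For an on-schedule C2D1 or C4D1 last dose, the 21-day rule reaches the cut only with all 21 days credited, so the category shift needs k ≥ 20.

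**The case against.** The strongest objection is about reach, not arithmetic. Duration is a descriptive variable in an uncontrolled study planned for about 18 subjects and stopped early. It does not enter DLT, MTD or MAD, response rate, TTR, DOR or PFS. SAP 6.7 also summarizes the number of doses received and lists every injection date, so a reader could recompute duration. All of that stands.

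Three limits on size also stand. Seven days is a maximum, because death or cutoff can truncate it. On the nominal schedule only last doses at C2D1 or C4D1 change category. The 17% is the largest relative loss.

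How many subjects fall under the discontinued rule is an inference. The SAP keeps an on-treatment bullet and a data cutoff, and gives no counts. The inference is reasonable, since the SAP speaks of the study and not only its enrollment as stopped early, but the number reclassified could be zero.

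One could also argue that 14 was deliberate, to give less credit after stopping. This does not stand up well. No reason is stated, the cycle 1 constant is the same in both bullets, and death and cutoff already have their own terms.

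**Conclusion.** The definition is wrong as written. The two bullets contradict each other from cycle 2 on, and only the 21-day version agrees with the dosing schedule. Discontinued subjects with a cycle 2 or later dose have their exposure understated by up to 7 days, and by the full 7 when neither death nor cutoff falls within 19 days of the last dose. Under that condition and on-schedule dosing, those whose last dose is C2D1 or C4D1 are placed one category too low. That 21 is the intended value is inferred from the other three constants and the schedule; the documents do not say so. The consequence is confined to the exposure table and the duration plot, but the correction is plain and worth making.

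**What to change.** In the discontinued-subject bullet of SAP 6.7, replace 14 days with 21 days for last doses at C2D1 or later, leaving the cycle 1 constant and the death and cutoff terms as they are. If 14 was intended, state the reason there and in a footnote to Table 14.3.1.1 and Figure 14.2.1. This changes an analysis derivation only and touches no dosing or clinical rule. The cost is one number in the SAP and one line of code, and it belongs before Database Freeze, the point by which SAP 1 says analysis decisions are settled.

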6.8 Concomitant Medications

Concomitant medications will be mapped to Anatomical Therapeutic Chemical (ATC) class and Generic Drug Names using the WHO Drug Dictionary. Concomitant medications will include medications taken on or after the date of the first dose of study drug. Any medications that are started prior to the date of the first dose but continued beyond the date of first dose will be counted as concomitant medications. Concomitant medications along with dose, route, start/end date, and indication for each medication will be presented in a data listing.

6.9 Concomitant Procedures

Concomitant procedures include cancer-related or treatment-related procedures or palliative radiotherapy that is administered while on study therapy. Concomitant procedures along with start/end date and indication for the procedure will be presented in a data listing.

7. EFFICACY ANALYSES

The efficacy endpoints include objective response, TTR, DOR, PFS, and change from baseline lesion diameter for injected lesion and non-injected lesions. All efficacy endpoints are based on the investigator disease assessment per RECIST 1.1. The efficacy analyses will be based on the All Treated population and Response Evaluable population. Unless specified otherwise, all efficacy data summaries will be presented by dose levels/cohorts, cancer type and all subjects in the analysis population.

Disease assessment will be performed at baseline (screening visit) and at the following intervals until disease progression: every 6 weeks until week 54, every 12 weeks up to year 2, and every 24 weeks until study conclusion. Confirmatory scans should be performed at least 4 weeks (>28 days) after initial documentation of an objective response and preferably at the next scheduled disease assessment that is 6 weeks later. If subjects discontinue study treatment prior to progressive disease, they should continue to be followed with radiologic disease assessments until disease progression, start of a new anti-cancer therapy, withdrawal of consent or death, whichever is earlier.

7.1 Objective Response Rate

The ORR is defined as the proportion of subjects whose best overall response is a confirmed CR or confirmed PR based on investigator assessment according to RECIST 1.1. The ORR will be estimated with a 95% CI using the exact probability method. The number and percent of subjects with the best overall response of CR, PR, SD, PD and not evaluable (NE) will be summarized. Summary of objective response will be provided for the All Treated population and Response Evaluable population.

The best overall response based on RECIST 1.1 is defined as the best overall response among all post-baseline timepoint assessments until the first PD per RECIST 1.1 or start of new anti-cancer therapy, whichever is earlier. For subjects who have not met the criteria for PD per RECIST 1.1

or have not started a new anti-cancer therapy, the best overall response is defined as the best overall response among all post-baseline timepoint assessments.

Based on the investigator assessment of overall response per RECIST 1.1 at post-baseline assessments, the best overall response will be determined programmatically as the following and

Table 3:

- CR > PR > SD > PD > NE
- CR = at least two determinations of CR with at least 4 weeks apart before progression.
- PR = at least two determinations of PR or better with at least 4 weeks apart before progression (and not qualifying for CR).
- SD = at least one SD or better \geq 35 days after the first dose and before progression (and not qualifying for a CR or PR). The minimum interval from the first dose date for the best response of SD is 6 weeks minus 7 days to allow for visit windows of \pm 7 days (35 days).
- If the minimum interval for SD is not met, the best response will depend on the subsequent assessments. See table 3 for details.
- PD is considered the best overall response when PD is documented and a best overall response of CR, PR, or SD could not be established before documentation of PD. Clinical progression will not be considered as documented disease progression in the determination of the best overall response.
- NE is considered the best overall response when PD has not been documented and a best response of CR, PR or SD could not be established.

Table 3. Best overall response when confirmation of CR and PR required.

Overall response First time point	Overall response Subsequent time point	BEST overall response
CR	CR	CR
CR	PR	SD, PD or PR ^a
CR	SD	SD provided minimum criteria for SD duration met, otherwise, PD
CR	PD	SD provided minimum criteria for SD duration met, otherwise, PD
CR	NE	SD provided minimum criteria for SD duration met, otherwise, NE
PR	CR	PR
PR	PR	PR
PR	SD	SD, provided minimum criteria for SD duration met, otherwise, PD
PR	PD	SD provided minimum criteria for SD duration met, otherwise, PD
PR	NE	SD provided minimum criteria for SD duration met, otherwise, NE

Overall response First time point	Overall response Subsequent time point	BEST overall response
NE	NE	NE

The best percent change from baseline in target lesion sum of diameters is defined as the largest reduction or smallest increase (in the case where a reduction does not occur) from baseline observed over all post-baseline disease assessments and will be presented using a waterfall plot.

Target lesion, non-target lesion, new lesion and response assessments will be presented in data listings. The percent change from baseline/nadir in target lesion sum of diameters will be kept 2 decimal places (xx.xx%) in the data listing and rounding is not required.

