4. ANALYSIS POPULATIONS

Population	Description
Enrolled	All subjects who have signed the main study informed consent form.
Screen Failures	All subjects who have signed the informed consent but have not received any dose of SL-172154.
All Treated	All subjects who receive at least one dose of SL-172154. Safety data will be evaluated based on this population.

Population	Description
DLT Evaluable	All subjects in the All Treated population 1) who have received at least 2 of the 3 scheduled doses of SL-172154 during cycle 1 and completed the safety follow up through DLT evaluation period; or 2) who experienced any DLT during the DLT evaluation period. The DLT evaluation period is defined as the first 21 days. The DLT evaluable population will be used to guide dose escalation and to determine the MTD or MAD.
Response Evaluable	All subjects in the All Treated population who have a baseline disease assessment and have at least one post-baseline disease assessment or had progressed or died before the first post-baseline disease assessment.

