7.4 Progression Free Survival

The PFS is defined as time from the first day of treatment to the first documented disease progression per RECIST 1.1 or death, whichever occurs first. Subjects who have not progressed at the time of analysis will be censored at the latest date of assessment from their last evaluable disease assessment. The censoring guidance and the date of PD/death or censoring are given in the

Table 4. PFS will be summarized using Kaplan-Meier method if data warrants. Individual PFS will be listed for the All Treated population.

Table 4. Summary of Censoring Guidelines for PFS based on RECIST1.1

Situation	Date of PD/Death or Censoring	PFS Outcome
Documented PD or death	Date of the PD or death, whichever comes first	Event (unless the censoring rule specified below)
Death or PD immediately after ≥ 2 consecutive missed or non-evaluable disease assessments ¹ as per the protocol specified assessment schedule	Date of last evaluable disease assessment prior to missed or non-evaluable assessments, or the first dose of investigational product, whichever occurred last	Censored
No PD or death at time of analysis or lost to follow-up	Date of last evaluable disease assessment	Censored
No baseline disease assessment OR no post-baseline disease assessment AND no death prior to second scheduled post-baseline disease assessment	Date of first dose	Censored

¹ Two or more consecutive disease assessments is defined as $\geq 16+1$ weeks for the first 6 months or $\geq 24+1$ weeks for 6-24 months (two disease assessments as per protocol plus a one week visit window) after the last evaluable post-baseline disease assessment. If a subject has two or more consecutive missed or non-evaluable assessments followed by an assessment showing no radiologic disease progression, then the assumption will be that the subject did not progress during the missed or non-evaluable assessments.

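### A subject with clinical progression, no post-baseline assessment and no death before week 12 is NE for best response and censored at first dose for PFS, like a subject with no outcome information

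*SAP*

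**What the plan says.** Four SAP rules meet in this case.

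- **Response Evaluable (SAP 4).** A treated subject with a baseline assessment qualifies if they "have at least one post-baseline disease assessment or had progressed or died before the first post-baseline disease assessment". The SAP does not say whether progression here means RECIST 1.1 progression, clinical progression or either.
- **Best overall response (SAP 7.1).** "Clinical progression will not be considered as documented disease progression in the determination of the best overall response". In addition, "NE is considered the best overall response when PD has not been documented" and none of CR, PR or SD could be established.
- **ORR denominator (SAP 5.3.1).** "Subjects with unknown or missing best response will be assumed to be non-responders and will be included in the denominator when calculating percentages".
- **PFS (SAP 7.4).** "The PFS is defined as time from the first day of treatment to the first documented disease progression per RECIST 1.1 or death", whichever is first. The last row of Table 4 censors at the date of first dose in this situation: "No baseline disease assessment OR no post-baseline disease assessment AND no death prior to second scheduled post-baseline disease assessment". Another row censors a death or PD that comes immediately after two or more "consecutive missed or non-evaluable disease assessments".

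SAP 7 schedules assessments every 6 weeks until week 54. It continues them after treatment stops, until progression, new anti-cancer therapy, withdrawal of consent or death. PFS is an exploratory objective, and Kaplan-Meier is planned only if the data support it.

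**The concern.** A subject can enter the Response Evaluable population because they progressed and then be reported there as not evaluable. For PFS the same subject contributes no follow-up: Table 4 treats them like someone who was dosed once and never heard from again. The trial does know something about them, namely that the investigator stopped treatment because the disease was getting worse.

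Kaplan-Meier estimation assumes that censored subjects have the same prognosis as those still at risk. A subject censored because clinical failure came before the first scan does not. Removing such subjects at time zero leaves a risk set with a better prognosis, and the curve moves up. In a trial of about 18 subjects, a few cases are enough to show. In the response tables, NE would mix subjects known to be failing with subjects whose status is unknown.

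**Working it through.** **1. Planned size.** Four dose levels × 3 subjects + 6 in the pharmacodynamic cohort = 18, which matches SAP 3.3. The second scheduled assessment falls at 2 × 6 = week 12.

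**2. The rules applied to one subject.** Suppose a subject stops at week 4 for clinical progression, has no post-baseline assessment and is alive at week 12.

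| Rule | Outcome |
|---|---|
| SAP 4, Response Evaluable | Included, if progressed covers clinical progression |
| SAP 7.1, best response | NE |
| SAP 5.3.1, ORR | Non-responder, kept in the denominator |
| SAP 7.4, Table 4, last row | Censored at first dose |

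**3. Can this happen?** Yes. Assessments end when new anti-cancer therapy starts (Protocol 3.14, SAP 7), so a subject who switches before week 6 need never be scanned. Protocol 8.2 does not allow treatment past progression in subjects with clinical symptoms of progression. Inclusion criterion 8 requires a life expectancy above 12 weeks, so survival to week 12 is expected for many.

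**4. Effect on week-12 PFS.** The documents give no rates, so these inputs are assumptions. Of N = 18, *k* subjects are as in step 2 and *r* = 18 − *k* are the others. Of the others, *d* have RECIST PD at week 6 and the rest are event-free past week 12. *d* is 30% or 50% of *r*, rounded (halves to the even number).

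- SAP rule: the *k* subjects leave the risk set before any event, so PFS = 1 − *d*/*r* = (*r* − *d*)/*r*.
- Clinical progression counted as an event at week 4: PFS = (1 − *k*/18) × (1 − *d*/*r*) = (*r* − *d*)/18.
- The first figure is the second multiplied by 18/(18 − *k*).

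| PD share | k | r | d | SAP rule | Counted as event | Shift (points) |
|---|---|---|---|---|---|---|
| 30% | 1 | 17 | 5 | 12/17 = 70.6% | 12/18 = 66.7% | 3.9 |
| 30% | 2 | 16 | 5 | 11/16 = 68.8% | 11/18 = 61.1% | 7.6 |
| 30% | 3 | 15 | 4 | 11/15 = 73.3% | 11/18 = 61.1% | 12.2 |
| 30% | 4 | 14 | 4 | 10/14 = 71.4% | 10/18 = 55.6% | 15.9 |
| 50% | 1 | 17 | 8 | 9/17 = 52.9% | 9/18 = 50.0% | 2.9 |
| 50% | 2 | 16 | 8 | 8/16 = 50.0% | 8/18 = 44.4% | 5.6 |
| 50% | 3 | 15 | 8 | 7/15 = 46.7% | 7/18 = 38.9% | 7.8 |
| 50% | 4 | 14 | 7 | 7/14 = 50.0% | 7/18 = 38.9% | 11.1 |

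**5. Effect of the death exception.** Take *k* = 4 and a 30% PD share. If two of the four die at week 10, the SAP rule gives (12/16) × (10/12) = 62.5% against 55.6%, a shift of 6.9 points. If all four die before week 12, it gives (14/18) × (10/14) = 55.6%, and the shift is zero.

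**6. ORR.** NE and PD are both non-responses in the same denominator, so relabelling one as the other leaves ORR and its exact interval unchanged.

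**The case against.** The strongest reply is that the plan applies its own definition consistently. Protocol and SAP define PFS by RECIST 1.1 progression or death, so leaving undocumented clinical progression out follows from that definition. Four further points limit the concern.

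- **Progression before the first assessment need not be clinical.** A reader might infer that it must be. Protocol 8 ties the first assessment to week 6 and allows more frequent ones. Superficial lesions may be measured by caliper or ruler (Protocol 8.1), and new lesions are PD. RECIST PD before week 6 is therefore possible. SAP 4 does not use the word clinical, so the clash with SAP 7.1 depends on how one undefined word is read.
- **Early failures as a group do not drop out of PFS.** A reader might infer this too. Death before the second scheduled assessment falls outside the last row of Table 4. Protocol 3.9 and 6.7 and SAP 7 call for continued assessment after treatment stops, so many clinical progressors would be scanned and become dated PD events. The exception is PD found only after two or more missed assessments.
- **Table 4 does cover the case.** Its last row applies. The issue is that the row does not separate this subject from one with no information.
- **The biased curve may never be drawn.** SAP 1 says enrollment stopped prematurely. The SAP output list has no PFS table or figure, only Listing 16.2.6.6, and discontinuation is listed by subject (Listing 16.2.1.2).

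All four points stand, and they narrow the concern to a small subgroup. They do not remove it. For that subgroup the censoring is informative, no planned analysis shows its effect, and the NE line in Tables 14.2.1 and 14.2.2 would still hide known failures.

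**Conclusion.** The point holds for subjects who meet three conditions together: they stopped for clinical progression, had no post-baseline assessment, and did not die before the second scheduled assessment. For them, best response is NE and PFS is censored at first dose, and any Kaplan-Meier PFS estimate is biased upward. The illustrative size is about 3 to 16 points at week 12 for 1 to 4 such subjects of 18, and zero if they die before then. The counts and PD rates are assumptions. With fewer than 18 treated, the same *k* would weigh more, because the inflation factor is N/(N − *k*).

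The documents do not support reading this as an error in the RECIST-based definition, as a bias in ORR, or as a general loss of early failures from PFS. Because PFS is exploratory and planned only as a listing, this is a low-cost improvement to reporting.

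**What to change.** Keep the RECIST 1.1 analyses as planned, and make four additions.

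1. SAP 4: state whether progressed, in the Response Evaluable definition, includes clinical progression.
2. Tables 14.2.1 and 14.2.2: show clinical progression with no post-baseline assessment on its own line, apart from other NE.
3. Listing 16.2.6.6: flag these subjects, so that censoring at first dose is not read as absence of information.
4. SAP 7.4: if Kaplan-Meier PFS is produced, add a sensitivity analysis that counts them as events on the recorded clinical progression date, or on the treatment discontinuation date if none was recorded.

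The cost is a small amount of programming, and a softer, investigator-judged event in the sensitivity analysis only. A discontinuation date is only a stand-in for a progression date. SAP 6.1 already summarizes and lists the primary reason for stopping treatment, but neither document shows the eCRF categories, so the sponsor must confirm that clinical progression can be identified. If the database is already frozen, SAP 1 allows the change to be documented as a deviation in the study report.
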